14.0 SAFETY EVALUATION

Subjects must be evaluated by a physician or an appropriately trained healthcare professional at every study visit, and the evaluation must be documented. The procedures discussed below will be completed at the designated visits as outlined in [Section 11.0](#).

14.1 ADVERSE EVENTS

14.1.1 Adverse Event Definition

An AE is any untoward medical occurrence in a subject or clinical investigation subject administered a pharmaceutical product and which does not necessarily have to have a causal relationship with this treatment. An AE can, therefore, be any unfavorable and unintended sign (including an abnormal laboratory finding, for example), symptom, or disease temporally associated with the use of a medicinal product, whether or not considered related to the medicinal product (ICH-E2A guideline).

Adverse events may also include post-treatment complications that occur as a result of protocol-mandated procedures (e.g. invasive procedures such as venipuncture and biopsy). Pre-existing events that increase in severity or change in nature during, or as a consequence of, use of a medicinal product in a human clinical study will also be considered AEs.

Any preexisting medical condition or diagnosis associated with a clinically significant laboratory abnormality should be documented in the CRF.

An AE does not include the following:

- Medical or surgical procedures (e.g. surgery, endoscopy, tooth extraction, transfusion); the condition that necessitates the procedure is an AE. Any pre-existing medical condition that necessitates a procedure during the study should not be captured as an AE, and the condition should be listed in the medical history.
- Any pre-existing disease or condition or laboratory abnormality present or detected prior to the start of the study treatment regimen that does not worsen
- Laboratory abnormalities without clinical manifestations, which do not require medical intervention, or that do not result in termination or delay of study drug administration
- Situations where an untoward medical occurrence has not occurred (e.g. hospitalization for elective surgery, social and/or convenience admissions)
- Overdose of any study treatment or concomitant medication without any signs or symptoms, unless the subject is hospitalized for observation
- Progression of the index CABP or insufficient therapeutic effect of study drug, which is captured as an efficacy outcome (i.e., clinical failure at EOT or TOC)

- Progression of disease or insufficient therapeutic effect which causes new hospitalization (in subjects not previously hospitalized for the index CABP), rehospitalization (in subjects that were previously hospitalized for the index CABP and discharged); however, if this leads to death, it should be recorded as a serious adverse event (SAE) ([Section 14.1.3](#)).

A TEAE is defined as an AE or SAE that occurs during or after the first administration of study drug and up through the FU visit.

A life-threatening AE is an AE that, in the view of either the Investigator or Sponsor, places the subject at immediate risk of death. It does not include an AE that, had it occurred in a more severe form, might have caused death.

An AE is considered “unexpected” if it is not listed in the IB or is not listed at the specificity or severity that has been observed; or, if an IB is not available, is not consistent with the risk information described in the general investigational plan. For example, under this definition, hepatic necrosis would be unexpected (by virtue of greater severity) if the IB referred only to elevated hepatic enzymes or hepatitis. Similarly, cerebral thromboembolism and cerebral vasculitis would be unexpected (by virtue of greater specificity) if the IB listed only cerebral vascular accidents. “Unexpected,” as used in this definition, also refers to AEs that are mentioned in the IB as occurring with a class of drugs or as anticipated from the pharmacological properties of the drug, but are not specifically mentioned as occurring with the particular drug under investigation. Progressive worsening of the index CABP or insufficient therapeutic effect of study drug that leads to hospitalization or death (i.e., SAE criteria, [Section 14.1.4](#)) is considered expected—as part of potential disease progression—and not unexpected.

Some AEs are listed in the IB as occurring with the same class of drugs, or as anticipated from the pharmacological properties of the drug, even though they have not been observed with the drug under investigation. Such events would be considered unexpected until they have been observed with the drug under investigation.

The list of AEs included in the current version of the Investigator’s Brochure will be used as reference safety information.

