^lAt Screening, local laboratory evaluations required for assessing subject eligibility include serum transaminase (ALT and AST) and total bilirubin levels, serum creatinine and BUN (or urea), peripheral WBC count, absolute neutrophil count, coagulation, and immature neutrophil percentage. Blood will be collected for central laboratory testing at the Screening, Day 5, EOT and TOC visits (including serum β -HCG in females; full list of central laboratory tests available in [Appendix IV](#)); blood will also be collected for central laboratory testing at FU in subjects with clinically significant laboratory abnormalities noted at or after the TOC visit.

^mCollect blood for acute (Screening) and convalescent (TOC) atypical pathogen serology, including *Mycoplasma pneumoniae*, *Chlamydia pneumoniae*, and *Legionella pneumophila*, for central laboratory testing.

ⁿAt Screening, a urine dipstick will be performed locally; if results are abnormal and deemed clinically significant by the Investigator, a urinalysis will be sent to the central laboratory.

^oAt Screening, urine will be tested locally for *Streptococcus pneumoniae* and *Legionella pneumophila* using provided rapid antigen test kits.

^pAt Screening, local laboratory urine or serum pregnancy test (females only) is required to confirm study eligibility. In addition, blood will be collected from all female subjects for serum β -HCG pregnancy test by the central laboratory at the Screening and TOC visits.

^qAt Screening, collection of expectorated sputum or other deep respiratory sample should be attempted in all subjects. Gram stain will be performed on all sputum specimens and quality assessed. Culture will be performed on all adequate sputum samples or deep respiratory specimens. Post-baseline respiratory specimens should be collected as clinically indicated and from subjects who are clinical failures and require alternative antibacterial treatment for CABP ([Section 12.6](#)).

^rTwo sets of blood cultures (each set consists of 1 aerobic and 1 anaerobic blood culture bottle) will also be collected at Screening. Repeat post-baseline blood cultures should be collected on the day that the positive blood culture is detected. If subsequent blood cultures are also positive, repeat the blood cultures as necessary until negative blood cultures are obtained ([Section 12.6](#)).

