9.7 GUIDANCE TO INVESTIGATORS ON WHEN TO END STUDY DRUG THERAPY

The duration of study drug in this study is a fixed 7-day course in all three Treatment Arms; therefore, subjects who are improving clinically will receive no less or no more than 7 days of the study treatment regimen. At Day 7 (EOT), an assessment of clinical outcome will be performed by the Investigator. A subject will be determined as a clinical cure at EOT if the subject is alive and the infection is sufficiently resolved such that further antibacterial therapy is not needed ([Section 13.2.2](#)). Note that subjects with CABP may have some residual findings related to infection (i.e., cough) requiring non-antibiotic ancillary treatment (e.g., expectorant) at EOT and still meet criteria for clinical cure.

If additional antibacterial therapy is required for the index CABP (e.g., progressively worsening CABP between Day 1 and Day 7, or gradually improving CABP that requires additional antibacterial therapy beyond 7 days), study drug should be discontinued, the subject will be deemed a clinical failure on the day of study drug discontinuation, and open-label antibacterial therapy will be started at the discretion of the Investigator. Administration of blinded study drug will not be allowed beyond Day 7. In cases of premature discontinuation of study drug, subjects should not be discontinued from the study itself; subjects should remain in the study and undergo all scheduled assessments at EOT, TOC and FU ([Section 11.0](#)).

The Investigator may use culture and susceptibility results from the local microbiology laboratory to help guide therapy; however, decisions to continue or discontinue study drug should be based on clinical response rather than susceptibility results (as nafithromycin susceptibility testing is not available at the local site). If the index CABP is caused by a microorganism that is not susceptible to fluoroquinolones, macrolides, or ketolides in vitro, the decision to continue or discontinue study treatment should be based on the subject's clinical course and the Investigator's clinical judgment. These cases should be discussed with the Medical Monitor prior to prematurely discontinuing study drug, and the rationale for this decision should be recorded in the source documents.

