11.8 STUDY DAY 7 (END-OF-THERAPY [EOT])

Perform EOT assessments at any time during Day 7 after the final dose of study drug, or within 2 days following Day 7. Additional guidance on when to end study drug therapy is provided in [Section 9.7](#).

Administer study drug per the schedule in [Section 10.1](#).

Clinical Assessments:

- Record one set of vital signs, including body temperature (highest daily oral, rectal, or tympanic temperature), blood pressure, heart rate, respiratory rate, and pulse oximetry
- Perform a complete physical examination
- Assess CABP symptom severity ([Appendix III](#))
- Obtain a 12-lead ECG
- Identify, assess and record any AEs

- Record any concomitant medications
- Conduct clinical outcome assessment ([Section 13.2.2](#))

Central Laboratory Assessments:

- Obtain CBC, coagulation and chemistry panel ([Appendix IV](#))

Microbiological Assessments:

- If prior blood cultures are positive, repeated post-baseline blood cultures should be collected on the day that the positive blood culture is detected
- Repeated respiratory specimens should be obtained only if clinically indicated

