16.2.4 Safety Analyses

Evaluation of the safety and tolerability of oral nafithromycin for 3 or 5 days in the treatment of CABP is an important primary objective for this Phase II study. Safety will be analyzed in the Safety Population ([Section 16.1.1](#)). Subjects in the Safety Population will be analyzed according to the treatment actually received.

Safety will be evaluated by presenting summaries of AEs, physical examinations, vital signs, laboratory evaluations (hematology evaluation, chemistry panel, UA, and ECG parameters). For each safety parameter, the last assessment made prior to the first administration of study drug will be used as the baseline value for all analyses.

The incidence of TEAEs (defined in [Section 14.1.1](#)) will be presented by system organ class and preferred term according to MedDRA®, by relationship to the administration of study drug, and by severity. In addition, the incidence of SAEs and AEs leading to discontinuation of study drug will be presented by system organ class, preferred term, and relationship to study drug. If the incidence of SAEs and AEs leading to discontinuation of study drug is low, only a listing will be provided.

Descriptive statistics of vital signs at each time point measured, as well as the change from baseline and PCS changes, will be presented. Descriptive statistics for ECGs and physical examinations will also be presented for each time point measured. The number and percentage of subjects with a normal physical exam result at baseline and an abnormal physical examination result at a follow-up assessment will be provided for each time point. Descriptive statistics for clinical laboratory tests and vital signs and for the change from baseline will be presented by study visit. Potentially clinically significant clinical laboratory results will be determined based on normal limits and percent change from baseline.

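### The laboratory exclusion from adverse events does not require all of its conditions to hold, so an asymptomatic abnormality that needs treatment is not an AE once dosing has ended

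*Combined protocol and SAP*

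**What the plan says.** Section 14.1.1 opens with a broad definition under which an AE can be "any unfavorable and unintended sign (including an abnormal laboratory finding, for example), symptom, or disease". A list follows, introduced by "An AE does not include the following", and one of its bullets removes "Laboratory abnormalities without clinical manifestations, which do not require medical intervention, or that do not result in termination or delay of study drug administration".

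On timing, Section 9.7 states "Administration of blinded study drug will not be allowed beyond Day 7", and Section 11.8 says "Perform EOT assessments at any time during Day 7 after the final dose of study drug, or within 2 days following Day 7". Footnote l to Table 3-1 sets the draws: "Blood will be collected for central laboratory testing at the Screening, Day 5, EOT and TOC visits". Follow-up (FU) is different in kind: "blood will also be collected for central laboratory testing at FU in subjects with clinically significant laboratory abnormalities noted at or after the TOC visit". Section 11.10 likewise makes the FU laboratory tests conditional on an earlier clinically significant abnormality.

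Section 14.1.1 counts TEAEs from the first dose through the FU visit. Section 16.2.4 tabulates "The incidence of TEAEs" by system organ class and preferred term, by relationship to study drug and by severity. The same section summarises laboratory values and changes from baseline by visit, and identifies potentially clinically significant results.

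**The concern.** An exclusion of this kind is normally meant for incidental findings: no symptoms, no treatment and no effect on dosing. As drafted, the bullet does not say that all three must hold. The condition on stopping or delaying drug also cannot separate important from unimportant findings once there is no drug left to stop. A laboratory abnormality that was treated can therefore fall outside the AE definition only because it was found after the last dose.

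Safety and tolerability is one of the two primary objectives (Section 7.1). The investigator assesses relatedness and severity for AEs (Sections 14.1.2 and 14.1.3), so a finding that is not an AE receives neither and does not enter the TEAE tables. The bullet can be read in more than one way, so sites may also differ in what they record.

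**Working it through.** No sample size or event rate is involved. The check is of the logic of the bullet and of the timing of the draws.

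**Step 1. Logic.** Let A = no clinical manifestations, B = no medical intervention required, C = no termination or delay of study drug. Three readings are possible:

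- Literal: excluded if A or B or C.
- Narrower (A governs the bullet): excluded if A and (B or C).
- Conjunctive (what *and* would give): excluded if A and B and C.

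| A | B | C | Literal | Narrower | Conjunctive |
|---|---|---|---|---|---|
| yes | yes | yes | excluded | excluded | excluded |
| yes | yes | no | excluded | excluded | AE |
| yes | no | yes | excluded | excluded | AE |
| yes | no | no | excluded | AE | AE |
| no | yes | yes | excluded | AE | AE |
| no | yes | no | excluded | AE | AE |
| no | no | yes | excluded | AE | AE |
| no | no | no | AE | AE | AE |
| **Excluded** | | | **7 of 8** | **3 of 8** | **1 of 8** |

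These are counts of logical cases, not frequencies of findings.

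**Step 2. After the last dose.** C is then always true, which leaves the four rows with C = yes. Excluded: literal 4 of 4, narrower 2 of 4, conjunctive 1 of 4. The row A = yes, B = no, C = yes is the asymptomatic abnormality that needs intervention while dosing is unaffected. It is excluded on both readings that keep the *or*, and is an AE only on the conjunctive reading.

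**Step 3. Which draws are affected.** For a subject who completes the 7-day course:

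| Central draw | Timing | Before the last dose? | Routine? |
|---|---|---|---|
| Day 5 | Day 5 | yes | yes |
| EOT | after the final dose on Day 7, or up to 2 days later | no | yes |
| TOC | Day 12 to 18 | no | yes |
| FU | Day 28 to 34 | no | no, conditional |

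The routine post-baseline draws are Day 5, EOT and TOC. Two of the three follow the last dose. FU mainly rechecks abnormalities already seen, so it is not counted as a point of first detection.

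**Step 4. Against the TEAE window.** Counting from Day 1 to FU on Day 28 to 34, the days after Day 7 number 28 − 7 = 21 to 34 − 7 = 27. That is 21/28 = 75% to 27/34 = 79% of the window. In that part of the window the third condition is always met.

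**Step 5. Whether another section repairs it.** None does. No separate rule says when a laboratory abnormality is to be recorded as an AE. Section 14.1.5 directs investigators to signs, symptoms and clinical evaluation, which does not bring an asymptomatic finding back in.

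**The case against.** The strongest reply is that this is loose drafting, that the intended meaning is probably conjunctive, and that laboratory safety has its own route to the report. Much of that stands.

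- A reader might infer that every laboratory abnormality after Day 7 is exempt. That holds only on the literal reading. The phrase on clinical manifestations attaches directly to the noun and can govern the whole bullet, in which case symptomatic abnormalities remain AEs. The literal reading also comes close to cancelling the opening definition, which names abnormal laboratory findings as possible AEs.
- A reader might count FU and say that three of four scheduled draws are affected. The FU draw is conditional on an abnormality already noted, so the routine count is two of three. Unscheduled local tests (Section 14.3) are a further chance of detection during dosing.
- A reader might infer that TEAE incidence is the main safety measure, or that the laboratory signal disappears. The synopsis lists TEAEs, laboratory evaluation, vital signs, physical examination and ECGs without ranking them, and Section 16.2.4 summarises laboratory values whatever their AE status. The blinded monitoring committee also reviews the safety laboratory data (Section 14.4).
- A reader might infer that treated liver or renal disease goes unreported. The bullet removes laboratory abnormalities. An accompanying symptom or disease is still an AE under the general definition.
- Nothing shows a bias between arms. The same rule applies to three blinded arms on the same 7-day schedule.

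These points limit the reach but do not remove the problem. The treated, asymptomatic abnormality found after dosing is excluded on both readings that respect the *or*. Laboratory tables cannot supply an investigator's relatedness or severity judgement that was never requested.

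**Conclusion.** The bullet is wrong as written, within a limited scope. At the least, it keeps out of the AE record asymptomatic laboratory abnormalities that required medical intervention but did not stop or delay dosing. During dosing that means findings treated while study drug continued. After the last dose it means all such findings. In subjects who complete dosing, the second group covers abnormalities first seen at 2 of the 3 routine post-baseline draws. The loss is in AE and TEAE classification, relatedness and severity, not in laboratory data.

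This assumes that sites apply the text as it stands. If every site read it conjunctively the loss would not arise, but nothing in the documents tells them to. The number of findings affected cannot be estimated, because the documents give no rate of laboratory abnormalities. The change is worth making because safety is a primary objective and the repair is small.

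**What to change.** Reword the bullet so that a laboratory abnormality is excluded only if all of the following hold: no clinical manifestation, **and** no medical intervention required, **and** no termination or delay of study drug. Add that once dosing has ended, the first two conditions decide.

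Asymptomatic, untreated findings after the last dose would still not be AEs. They remain visible in the laboratory summaries of Section 16.2.4, which fits the apparent purpose of the exclusion.

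The cost is a slightly higher laboratory TEAE count and a minor protocol amendment, with the approvals that Section 18.4 requires. No visit, sample or sample size changes.

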14.1.2 Relatedness to Study Drug

For each reported AE, the Investigator must make an assessment of the relationship of the event to the study drug using the following scale:

- **Unrelated:** The event is definitely not associated with administration of the study treatment, and is judged clearly due to causes other than the study treatment. Clinical failure of CABP due to insufficient therapeutic effect of study drug is also considered “unrelated” to study drug.
- **Related:** The event is possibly or probably associated with administration of study treatment. Possibly-related events follow a reasonable temporal sequence from administration of study treatment, but may be due to another cause and could also be reasonably explained by the subject's clinical state or other modes of therapy

administered to the subject. Probably-related events follow a reasonable temporal sequence from administration of the study treatment, but are not easily explained by another cause such as known characteristics of the subject’s clinical state or other treatment, and are confirmed by improvement after stopping the study treatment.

These criteria, in addition to good clinical judgment, should be used as a guide for determining the causal assessment. If the event is believed to be unrelated to the study treatment, then an alternative explanation should be provided.

14.1.3 Severity Assessment

The Investigator will be asked to provide an assessment of the severity of the AE using the following categories: mild, moderate, or severe ([Table 14.1.3-1](#)). This assessment is subjective and the Investigator should use medical judgment to compare the reported AE to similar types of events observed in clinical practice. *Severity*, which is a description of the intensity of manifestation of the AE, is distinct from *seriousness*, for which specific SAE criteria are met ([Section 14.1.4](#)).

Table 14.1.3-1: Severity Assessments of Adverse Events.

Mild	Symptom(s) barely noticeable to the subject or does not make the subject uncomfortable. The AE does not influence performance or functioning. Prescription drugs are not ordinarily needed for relief of symptom(s).
Moderate	Symptom(s) of a sufficient severity to make the subject uncomfortable. Performance of daily activities is influenced. Treatment of symptom(s) may be needed.
Severe	Symptom(s) of a sufficient severity to cause the subject severe discomfort. Severity may cause cessation of treatment with the drug. Treatment for symptom(s) needed.

Abbreviation: AE = Adverse event.

14.1.4 Serious Adverse Events

An SAE is any adverse experience that occurs from the signing of the informed consent to the FU visit and that results in any of the following outcomes:

- Death
- Life-threatening situation (subject is at immediate risk of death)
- Inpatient hospitalization or prolongation of existing hospitalization
- Persistent or significant disability/incapacity
- Congenital anomaly/birth defect in the offspring of a subject who received study treatment
- Events that jeopardize the subject sufficiently that medical or surgical intervention may be required to prevent one of the above outcomes. Examples may include, but are not limited, to:

- Intensive treatment in an emergency room for allergic bronchospasm
- Blood dyscrasias that do not result in hospitalization
- Seizures that do not result in hospitalization

Progression of disease or insufficient therapeutic effect which causes new hospitalization (in subjects not previously hospitalized for the index CABP), rehospitalization (in subjects that were previously hospitalized for the index CABP and discharged) is not a SAE; however, if this leads to death, it should be recorded as a serious adverse event (SAE) ([Section 14.1.3](#))

The Sponsor is required to inform worldwide regulatory authorities of SAEs that meet specific criteria. Therefore, the Sponsor must be notified immediately regarding any SAE that occurs after informed consent is obtained. All SAEs and follow-up information must be reported within 1 business day, or 24 h as required by local regulations, by faxing a completed SAE Report Form to the fax number below (Table 14.1.4-1) or emailing a completed SAE Report Form to the [REDACTED] at [REDACTED].

Table 14.1.4-1: Toll-free Safety Line Numbers for SAE Reporting*

Country	Toll-free Safety Line Numbers
Bulgaria	[REDACTED]
Georgia	[REDACTED]
Latvia	[REDACTED]
Republic of South Africa	[REDACTED]
Romania	[REDACTED]
	[REDACTED]
Russia	[REDACTED]
	[REDACTED]
	[REDACTED]
USA	[REDACTED]
	[REDACTED]
	[REDACTED]

*Any fax sent to these lines will be routed to [REDACTED].

Supplemental information for each SAE should be submitted as soon as available and may include laboratory results, radiology reports, progress notes, hospital admission and emergency room notes, holding and observation notes, discharge summaries, autopsy reports, and death certificates.

The Investigator is expected to take all therapeutic measures necessary for resolution of the SAE. Any medications or procedures necessary for treatment of the SAE must be recorded in the eCRF. All SAEs are to be followed until resolution or until the SAE is deemed stable. The Sponsor may contact the study center to solicit additional information or follow up on the event.

